7.10.8.6. Subgroup Analyses

Subgroup analyses are described in section 7.9.

7.10.9. Ancillary #6: AF burden over all follow-up after the blanking period

Compare the AF burden over all follow-up occurring after the blanking period between study arms.

7.10.9.1. Hypothesis

There is no pre-specified hypothesis for this objective.

7.10.9.2. Performance Criteria and Rationale

There are no performance criteria for this objective.

7.10.9.3. Endpoint Definition

The endpoint for this objective is the percent of time a subject is in AF over all of their follow-up after the blanking period.

Data obtained directly from the Reveal LINQ device will be used to calculate this endpoint in the following manner:

- Blanking period: 90 days after the cryoablation procedure
- Numerator: time in AF from Reveal LINQ device after the blanking period
 - Start date: Index cryoablation procedure date + 91
 - End date: End of follow-up time (latest date Reveal LINQ device data was recorded from study device data)
 - Numerator: The total amount of time (e.g., hours, days, etc.) the device shows the subject is in AF starting on the start date and ending on the end date
- Denominator: total follow-up time for a subject after the blanking period
 - Start date: Index cryoablation procedure date + 91
 - End date: End of follow-up time (latest date Reveal LINQ device data was recorded from study device data)
 - Denominator (days): End date – start date
 - Note: The denominator calculation assumes that the device will be monitoring for AF every day from when it is implanted to the latest date Reveal LINQ device data is recorded from the study device data. If it is possible that the device will not record 24 hours a day, 7 days a week, then we may need to use the device data to determine the total follow-up time where the device was monitoring for AF.
- Endpoint: (Numerator/Denominator) x 100

- Ensure time units for numerator and denominator are the same. The choice of denominator units will be made to most sensibly report the results, depending on how much time subjects are in AF (e.g., hours, days, etc.).

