### **6.14 LINQ insertion**

Before the subject is discharged from the hospital, preferable while still in the EP lab, insert the Reveal LINQ device. The insertion procedure will be performed in accordance with the hospital's standard practice and in accordance with the Medtronic Reveal LINQ manual. Program Device Data Collection parameters and verify device sensing performance is acceptable. Subjects with an existing Reveal LINQ device may be enrolled if they have a minimum of 1 year remaining battery life. Ensure the device is programmed to the settings below.

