### **6.20 System modification for Reveal LINQ**

A system modification will be reported in the event the Reveal LINQ requires invasive modification (e.g. reposition, explant, replacement). In the event of a system modification, the follow-up visit schedule for the subject will remain unchanged. If the device is explanted and a replacement will not be inserted, the subject should continue to stay in the study.

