## 8. STUDY DEVIATIONS

A study deviation is defined as an event within a study that did not occur according to the CIP or CTA.

Prior approval by Medtronic is expected in situations where the investigator anticipates, contemplates, or makes a conscious decision to deviate. Prior approval is not required when a deviation is necessary to protect the safety, rights or well-being of a subject in an emergency or in unforeseen situations beyond the investigator's control (e.g. subject failure to attend scheduled follow-up visits, inadvertent loss of data due to computer malfunction, inability to perform required procedures due to subject illness). A study deviation is not required if a subject misses a monthly LINQ manual interrogation.

All study deviations must be reported on the CRF regardless of whether medically justifiable, pre-approved by Medtronic, an inadvertent occurrence, or taken to protect the subject in an emergency.

In the event the deviation involves a failure to obtain a subject's consent or is made to protect the life or physical well-being of a subject in an emergency, the deviation must be reported to the IRB/MEC as well as Medtronic within five working days. Reporting of all other study deviations should comply with IRB/MEC policies and must be reported to Medtronic as soon as possible upon the center becoming aware of the deviation. Refer to Investigator Reports, Table 11 for specific deviation reporting requirements and timeframes for reporting to Medtronic and the applicable regulatory body(s).

Medtronic is responsible for analyzing deviations, assessing their significance, and identifying any additional corrective and/or preventive actions (e.g. amend the CIP, conduct additional training, or terminate the investigation). Repetitive or serious investigator compliance issues may result in initiation of a corrective action plan with the investigator and center, and in some cases, necessitate suspending enrollment until the problem is resolved or ultimately terminating the investigator's participation in the study. Medtronic will provide center-specific reports to investigators summarizing information on deviations that occurred at the investigational center on a periodic basis.

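### By default, the AF burden formula divides by calendar days, one day fewer than the numerator covers, and counts interior unmonitored time as AF-free; the correction is only optional

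*SAP*

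**What the plan says.** SAP 7.10.9.3 sets the endpoint: "The endpoint for this objective is the percent of time a subject is in AF over all of their follow-up after the blanking period". The blanking rule is "Blanking period: 90 days after the cryoablation procedure". Numerator and denominator share the same two dates. The start is the index procedure date plus 91, and the end is the latest date with Reveal LINQ data.

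- **Numerator:** total time the device shows AF, "starting on the start date and ending on the end date".
- **Denominator:** end date minus start date, in days.
- **Note to the denominator:** "The denominator calculation assumes that the device will be monitoring for AF every day from when it is implanted" up to the latest recorded date. If round-the-clock recording may not hold, "we may need to use the device data to determine the total follow-up time where the device was monitoring for AF".
- **Units:** both parts must use the same time unit, and the choice of unit is left open.

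SAP 7.10.9.4 takes each subject's score into a Mann-Whitney test, a Hodges-Lehmann estimate with a 95% confidence interval, and a median for each arm. Protocol 12.6 describes burden only as percent of time in AF, so it does not settle the denominator.

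On continuity of monitoring, Protocol 6.20 says "A system modification will be reported in the event the Reveal LINQ requires invasive modification (e.g. reposition, explant, replacement". It leaves the visit schedule unchanged after such an event.

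**The concern.** A percentage of time needs a numerator and a denominator over the same time. Here they differ in two ways.

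First, AF time is counted on both the start day and the end day, but subtracting the dates drops one of those days. The score can then exceed 100%, and it cannot be computed when the two dates coincide.

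Second, the numerator can only accumulate while the device is recording, whereas the denominator runs on the calendar. A gap inside the window adds follow-up but can add no AF, so burden is understated in proportion to the gap. If gaps differed between arms, part of that difference would appear in the ranks and in the Hodges-Lehmann estimate as a difference in burden.

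The SAP sees the second problem but leaves its remedy discretionary. It gives no trigger, no definition of monitored time and no point by which the choice must be made.

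**Working it through.** The documents give no numerical burden figure for this endpoint, so there is nothing to reproduce. The check applies the SAP formula directly.

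**Inputs.** Start is day 91 and the end is the last LINQ date (SAP 7.10.9.3). Day 180 is the 6-month reference day in SAP 7.10.1.4, and day 365 is the 12-month target in Protocol Table 6. The documents give no gap rate, so the gap sizes below are assumptions.

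**Step 1: the day count.** Let D = end − 91. The numerator window holds D + 1 days, so uninterrupted AF scores 100 × (D + 1)/D.

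| Last device date | Denominator D | Days in numerator window | Score |
|---|---|---|---|
| Day 91 | 0 | 1 | undefined |
| Day 180 | 89 | 90 | 101.1% |
| Day 365 | 274 | 275 | 100.4% |

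If data stop halfway through the last day, day 180 gives 89.5/89 = 100.6%, still above 100%. Changing units does not help: in hours, day 180 gives (90 × 24)/(89 × 24) = 2160/2136 = 101.1%.

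**Step 2: interior gaps.** Take a post-blanking window of 365 days, a burden of 10% in monitored time, and G unmonitored days before the last device date. Ignoring the day-count error, the default score is 10% × (365 − G)/365.

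- G = 30: 10% × 335/365 = 9.2%
- G = 60: 10% × 305/365 = 8.4%

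With the day-count error included, the divisor is 364. The results are 33.5/364 = 9.2% and 30.5/364 = 8.4%, the same after rounding.

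**Step 3: the two faults together.** They act in opposite directions. In continuous AF with data to day 180, one full gap day gives 89/89 = 100.0%. A score above 100% therefore needs less than one missing day.

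**Step 4: which gaps count.** Both windows close at the last LINQ date, so only a gap followed by later recording dilutes the score. Removal or loss of function followed by replacement, which Protocol 6.20 foresees, can produce one. Explant or battery depletion without replacement cannot, because both windows then end together.

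**Step 5: the corrected denominator.** With monitored time over the same inclusive window, continuous AF scores 100.0% at each date in the table, and a 10% burden stays 10.0% whatever the gap.

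**The case against.** The strongest reply is that the SAP already covers this. It discloses the continuous-monitoring assumption, and its note describes the right remedy, time during which the device was monitoring. That reply stands against any claim that the SAP overlooks gaps. It does not stand as a defense of the rule, because the note permits the remedy without requiring it.

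A reader might infer more from the protocol than it supports:

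- **Battery life.** Protocol 6.14 says "Subjects with an existing Reveal LINQ device may be enrolled if they have a minimum of 1 year remaining battery life", and Protocol 1.2 expects a study of about 57 months. Depletion without replacement ends both windows, however, and Protocol 6.24 allows exit at battery end of life after at least 6 months. It shortens follow-up and leaves no interior gap.
- **Missed interrogations.** Protocol 8 says "A study deviation is not required if a subject misses a monthly LINQ manual interrogation". The change history in Appendix I (version 13.0) gives the reason: nightly automatic transmissions can be reviewed. A missed manual interrogation is not in itself lost monitoring.
- **Unequal monitoring between arms.** Nothing in the documents shows it. Both arms receive the same device, required programming and transmission schedule.
- **A choice made knowing the results by arm.** SAP 5.3 holds analyses by actual assignment until the final freeze, apart from interim and DMC work, and the note's condition concerns recording, not outcome. The fair criticism is that the choice is undefined, not that it would be steered.

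It is also fair to say that the day-count error is small. It multiplies every score by (D + 1)/D, about 1.1% in relative terms at day 180 and 0.4% at day 365. It leaves zero burdens at zero and will hardly move a rank test. An impossible percentage could also be caught in the Level II peer review that SAP section 8 requires for ancillary programs.

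**Conclusion.** The point holds, at minor severity. As written, the default denominator matches neither the numerator's window nor the monitored time, so the rule can return a wrong value. The day-count error is certain from the text, provided both end dates are counted as the SAP words it, and it is about 1% or less from day 180 onward. The gap effect is potentially larger: 10% read as 9.2% or 8.4% in the examples. Its actual size is unknown, because the gap lengths are assumed and the documents give no rate of interrupted monitoring.

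The documents do not support saying that all unmonitored time counts as AF-free. That is true only of the default formula, and only of gaps before the last device date. No success decision depends on this endpoint: it is ancillary, with no hypothesis and no performance criterion.

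**What to change.** Amend SAP 7.10.9.3 as follows:

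- Define the denominator as the total time the device was monitoring for AF, with AF-free monitored time included, from procedure date + 91 to the last device date, both days included. Use exactly the same window for the numerator. Where monitoring is complete, this equals end − start + 1.
- Make the monitored-time rule mandatory by replacing the note's "may need to" wording with a plain statement that device data will be used.
- Report monitored days by arm beside the burden results, and state how a subject with no monitored time after blanking is handled.

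The cost is SAP wording and minor programming. The calculation already draws on Reveal LINQ device data, so no new data collection is needed.

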7.10.9.4. Analysis Methods

The Mann-Whitney U test will be used to compare the AF burden between study arms. This non-parametric test is used rather than the Student's t-test since AF burden tends to have a skewed distribution with many values near zero. The difference in AF burden will be characterized by the Hodges-Lehmann estimator, the median of all pairwise differences in AF burden between study arms. Pairs consist of one subject from each study arm. The pairwise difference is calculated by taking the difference of AF burden between the subjects in each pair. The total number of pairs is equal to the number of subjects receiving both renal artery denervation and pulmonary vein isolation within one procedure times the number of subjects receiving only pulmonary vein isolation.

The following will be reported:

- The median AF burden for each study arm
- Value of U statistic
- Number of subjects in each study arm analyzed for this objective
- Significance level (p-value from Mann-Whitney U test)
- Hodges-Lehmann estimator (estimates treatment effect)
- 95% confidence interval for Hodges-Lehmann estimator

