#### **12.4.3 Rationale for Performance Criteria**

In the STOP-AF trial, subjects randomized to receive cryoablation had a 6- month chronic treatment success rate of 75.0%. In the patient population of this feasibility study, including patients with either paroxysmal AF or persistent AF and with uncontrolled hypertension, the rate of chronic treatment success is expected to be lower. Also, use of intensive AF monitoring with the Reveal LINQ device has the potential to identify patients with recurrent AF that might not be detected with periodic trans-telephonic and Holter monitoring, as was performed in the STOP-AF trial, leading to a lower rate of chronic treatment success. In the treatment arm, the addition of the renal artery denervation procedure to the pulmonary vein isolation procedure for treatment of AF has the potential to increase the rate of chronic treatment success. While it's uncertain to what degree these factors may affect the rate of chronic treatment success, this feasibility study is designed to be able to identify a difference in chronic treatment success rate if the rate through 6 months is at least 75% in the Treatment arm and 50% in the Control arm through 6 months.

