5.6. Data Monitoring Committee

A DMC will periodically review accumulating safety data for the study, including the rate of safety composite events within each study arm and the difference in the rate between study arms (i.e., the Primary Safety Objective).

6. Determination of Sample Size

The overall study sample size is 70 randomized subjects that undergo a pulmonary vein isolation procedure which is the required sample size for the primary effectiveness objective.

Subjects that are enrolled in the study may not go on to be randomized due to a variety of reasons, including elective withdrawal prior to randomization, blood pressure measurements that do not meet study criteria, or renal anatomy that is found to be ineligible upon angiography. Based on the rate of randomization among enrolled subjects in trials with similar screening criteria, up to 245 subjects may need to be enrolled and undergo screening in order to ensure that 70 subjects are randomized.

There will be at least 78% power to test the primary effectiveness objective provided at least 70 subjects undergo randomization and undergo a pulmonary vein isolation procedure. Table 1 below shows the expected incremental power at each analysis. The first and second look correspond to the interim analyses. The third interim look is the final analysis.

Table 1: Power at each stage of the analyses

Look	Patients w/ six month follow-up	Expected Incremental Power of Analysis
1	32	17.6%
2	50	10.1%
3	70	50.9%
Cumulative Power:		78.6%

Subjects who are randomized and meet either of the following two conditions do not count toward the 70 randomized subjects to be used in the mITT set (define below):

- Exit the study without undergoing a pulmonary vein isolation procedure
- Subjects who are randomized to the treatment group and are found not to meet inclusion/exclusion criteria during the renal denervation procedure

The sample size calculation is based on the following assumptions:

- 1:1 randomization
- Constant randomization rate over 16 months
- Last enrolled subject followed through 6 months post-procedure
- 50% chronic treatment success in the Control arm (PVI only) versus 75% in the Treatment arm (equivalent to a hazard ratio of 0.415) through 6 months post-procedure
- Constant hazard ratio over all follow-up
- Constant attrition (dropout) of 5% per 6 months

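### AF burden (ancillary objective 6): the denominator is up to one day short, and the Hodges-Lehmann estimate needs companion effect measures because many burdens will be at or near zero

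*SAP*

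**What the plan says.** **Endpoint (SAP 7.10.9.3).** Burden is the percentage of time in AF over all of a subject's follow-up after blanking. The start date is the index cryoablation date plus 91, and the end date is the last date with LINQ data. The numerator is device-recorded AF time "starting on the start date and ending on the end date". The denominator is given as "Denominator (days): End date – start date". A note allows monitored device time to be used if recording turns out not to be continuous.

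**Analysis (SAP 7.10.9.4; the same method is in protocol 12.6).** Arms are compared with the Mann-Whitney U test, chosen because burden is skewed and concentrated close to zero. On the effect measure the section states: "The difference in AF burden will be characterized by the Hodges-Lehmann estimator, the median of all pairwise differences in AF burden between study arms". The listed outputs are the median per arm, U, the number of subjects per arm, the p-value, and the Hodges-Lehmann estimate with its 95% CI.

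**Design rates.** Protocol 12.4.3 designs for success of "at least 75% in the Treatment arm and 50% in the Control arm through 6 months". SAP section 6 repeats this as "50% chronic treatment success in the Control arm (PVI only) versus 75% in the Treatment arm (equivalent to a hazard ratio of 0.415", and assumes "Constant hazard ratio over all follow-up" and "1:1 randomization". On size it says: "The overall study sample size is 70 randomized subjects that undergo a pulmonary vein isolation procedure".

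**The concern.** There are two separate matters.

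1. **Day count.** The numerator covers both end days of the interval, but the denominator is a plain date difference. A percentage of time should not be able to exceed 100%.

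2. **Effect measure.** A chronic treatment success has no documented LINQ AF episode after day 90, so its burden should be zero or close to it. The SAP uses this feature to choose the test but not the effect measure. When both arms have a large mass at zero and the masses differ, no single location shift describes the contrast. The median pairwise difference can then sit at or near zero while mean AF time differs clearly. The study is meant to inform a pivotal trial (protocol 12.4.2), and burden was one reason for adopting the LINQ (protocol change history, version 6.0). An effect that cannot be read as AF time removed is less useful for that purpose.

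**Working it through.** **1. Denominator.** For data ending on day F, the days from 91 to F inclusive number F - 91 + 1, and the SAP divides by F - 91. The maximum burden is (F - 90)/(F - 91):

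| Last data day | Inclusive days | SAP denominator | Maximum burden |
|---|---|---|---|
| 180 | 90 | 89 | 101.1% |
| 365 | 275 | 274 | 100.4% |
| 730 | 640 | 639 | 100.2% |

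If data end on day 91 the denominator is 0. If the last date is only partly recorded, the shortfall is less than one day.

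**2. Reproducing the plan's event counts.** These give the event-free shares over all follow-up.

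- Hazards per month: control ln(2)/6 = 0.1155; treatment -ln(0.75)/6 = 0.0479. Their ratio is 0.415, as stated.
- Dropout of 5% per 6 months: d = -ln(0.95)/6 = 0.00855.
- Accrual over 16 months gives follow-up u uniform on 6 to 22 months.
- Event probability = average over u of [h/(h+d)] × [1 - exp(-(h+d)u)]: control 0.739, treatment 0.451.
- Times 34.5 per arm: 25.5 and 15.5 events, against 25 and 16 in the EaST output.
- Event-free shares from EaST: control 1 - 25/34 = 26%; treatment 1 - 16/35 = 54%.

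**3. Signs of the pairwise differences (treatment minus control).** Assume event-free subjects have burden exactly 0 and failures have the same continuous burden distribution in both arms. Let a and b be the zero shares in treatment and control.

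- Zero: ab
- Negative: a(1-b) + (1-a)(1-b)/2
- Positive: (1-a)b + (1-a)(1-b)/2

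| Zero shares (T, C) | Negative | Zero | Positive | Median difference |
|---|---|---|---|---|
| 0.75, 0.50 (6-month rates) | 43.75% | 37.5% | 18.75% | exactly 0 |
| 0.543, 0.265 (EaST counts) | 56.7% | 14.4% | 28.9% | below 0 |

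**4. Simulated behaviour.** 35 per arm, lognormal burden in failures, two-sided 0.05 (assumed, since the SAP sets no alpha for this objective):

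| AF-free (T, C) | Hodges-Lehmann = 0, all trials | Hodges-Lehmann = 0, trials with p<0.05 |
|---|---|---|
| 75%, 50% | about 78% | about 60% |
| 65%, 40% | about 53% | not tabulated |
| 54%, 26% (EaST counts) | 15-18% | under 1% |
| 35%, 14% (51-month accrual) | about 10% | 0% |

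**5. Size at 54% and 26%.** With failure median 1% and log-SD 1.5, mean burden in failures is exp(1.5²/2) = 3.08%. The expected mean difference is 3.08 × (16/35 - 25/34) = -0.86 points; simulation averages are about -0.82. The typical Hodges-Lehmann estimate is about -0.18, roughly a fifth to a quarter of that. The treatment-arm median is exactly 0 in about 70% of trials.

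**The case against.** **A stronger reading is tempting.** From the 75% and 50% rates a reader might infer that the Hodges-Lehmann estimate will be 0 in most trials even when the test is significant. The documents do not support this. Those rates apply through 6 months, whereas burden runs over all follow-up, and the plan assumes a constant hazard ratio with follow-up until the last subject reaches 6 months. Under its own event counts, a zero estimate beside p<0.05 almost never occurs. This part of the objection stands.

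**Exact zeros are an assumption.** The SAP speaks of values near zero. Burden comes straight from device data, and the protocol lists over-sensing as a LINQ risk. Traces of false detection would break the ties. That stands too, although the estimate would still be very small.

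**Much of the remedy is already there.** U and the numbers per arm are listed, so U/(n1·n2) needs one division. Protocol 12.6 calls for means of continuous ancillary variables. The primary Kaplan-Meier analysis largely covers freedom from AF. What is missing is confidence intervals for these contrasts and their explicit use as effect measures for burden.

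**Hodges-Lehmann is standard.** It is the usual companion to Mann-Whitney, and as a median pairwise difference it has meaning without a shift model. This is a reason to keep it, not a reason to report it alone.

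**One day is trivial.** The relative error is about 1.1% at day 180, less later, and similar in both arms. Much larger excesses arise only if data stop within days of the end of blanking (for example, 10/9 = 111% at day 100). A reader should not infer a material bias between arms. The rule is still wrong as written, and the SAP's note on non-continuous recording does not address the day count.

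**Conclusion.** The concern holds in a limited form.

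- **Denominator:** it is up to one day short, so continuous AF can give more than 100%. The error is small and similar in both arms.
- **Effect measure:** Hodges-Lehmann is the only between-arm effect listed for a zero-heavy endpoint. How it behaves depends on how far recurrence continues after 6 months. It is exactly 0 in about 78% of trials if AF-free shares stay near 75% and 50%, but in only 15-18% at the plan's all-follow-up counts. In the second case it is usually non-zero but far smaller than the mean difference (about -0.18 against -0.82 points).

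These figures rest on zero burden in event-free subjects, a lognormal burden in failures with an assumed median of 1%, and a 0.05 level; none of these is in the documents. The objective is ancillary, with no hypothesis or performance criterion, and the primary conclusion is not affected.

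**What to change.** - **SAP 7.10.9.3:** change the denominator to end date minus start date plus 1, or use monitored device time over the identical interval for both numerator and denominator. The second option also handles a partial last day.
- **SAP 7.10.9.4:** keep Mann-Whitney and Hodges-Lehmann with its CI. Add (a) U/(n1·n2) with a 95% CI; (b) the share of subjects with any post-blanking AF time in each arm; and (c) the difference in the mean burdens already planned under protocol 12.6, with a bootstrap CI.

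The cost is a few lines of SAP text and code, with no new data. The downside is that the mean difference is sensitive to a few high-burden subjects. The bootstrap interval will help to show this, and the rank-based measures beside it are less affected.
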